1.2 Secondary Objectives

Hypotheses:

1. Veterans in the intervention group will have significantly reduced health care costs, as compared to the control group, by the end of the 24-month study
2. The immunosuppressant dashboard system will provide near real-time, actionable alerts that will allow the pharmacist to conduct timely interventions on potential or ongoing drug-related problems

Objectives:

1. 24-month estimated health care costs, compared between the intervention and usual care groups
2. Estimated graft survival rates, compared between the intervention and usual care groups
3. Estimated patient survival rates, compared between the intervention and usual care groups
4. Potential medication safety issues, defined as the proportion of patients with the following, based on automated reports for the transplant medication dashboard:
 - a. Percent of patients with missing labs
 - b. Percent of patients alarming lab values without follow up scheduled
 - c. Immunosuppression adherence, estimated using the proportion of days covered (PDC)

- d. Percent of patients on significant drug interaction without a immunosuppressant level
- e. Percent of patients with hospital discharge or ED visit without follow up scheduled
- 5. Proportion of alerts that were deemed clinically relevant and actionable by the intervention pharmacists
- 6. Proportion of interventions that were deemed to be accepted when made to other providers based on dashboard reporting information
- 7. Average time required to respond to each alert

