5.2 Training for Study Interventions

Prior to the initiation of the study, the pharmacists randomized to the intervention will participate in a two-day training conference held at the coordinating site. During this training, the dashboards functionality will be reviewed, along with the SOP manual which fully guides interventions. During this training conference, the intervention pharmacists will also participate in case-based competencies.

Sessions that occur during this conference include:

1. General overview of organ transplantation
2. Review of immunosuppression pharmacology and pharmacokinetics
3. Review of transplant immunosuppression dashboard specifics
4. Running reports to create alerts
5. Assessing clinical relevance of alerts
6. Alert categories
7. Interventions to address alerts
8. Suppressing alerts
9. Clinical and research documentation
10. Motivational interviewing techniques – face-to-face and over the phone
11. Provider collaboration strategies
12. Case-reviews

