Another secondary outcome is to assess the success of the dashboard systems expansions and utilization. To do so, we will evaluate the dashboard's functionality by measuring and reporting descriptive statistics for the alert numbers, alert relevance, time and the actions taken with regards to the alert and the intervention magnitude. We will measure and report the time effort needed to conduct the interventions by study site pharmacists. Using REDCap, we will build an electronic data capture system, which allows the intervention pharmacists to efficiently enter alert and intervention information through a web-based portal, which will be housed within the VINCI environment. This information will be captured during the first 12 months of the intervention period, which will provide ample data without overwhelming the clinical pharmacists throughout the 24-month study. These measures will allow us to ascertain if the expanded dashboard is meeting expectations, with regards to functionality and efficiency. These measures will be assessed by investigators at quarterly intervals. If there is strong evidence to suggest particular components of the dashboard are not providing clinically relevant alerts or if the ratio of alerts to actionable alerts is exceedingly high, then the investigational team may decide to modify this component of the system. Thus, these

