process measures will serve to both assess the dashboard functionality and allow for modification to improve the efficiency of the intervention. The time assessment data will allow us to determine the amount of time and effort implementing this system requires, as it relates to embedding it into normal workflow processes. This information will be important if the dashboard is deemed effective and is disseminated for use to across the VA, as it will allow administrators to accurately assess the required pharmacist time needed for implementation. Finally, we will assess the type and magnitude of the interventions made using this dashboard to ensure study fidelity. The categorization and magnitude of these interventions will be assessed using the Overhage criteria, which is a well-established and validated method used in numerous studies, included several published by the investigators proposing this study.⁵² We will also assess the number of potential immunosuppression safety issues that occur and compare these between the two study arms. To do so, we will use the dashboard to provide monthly measurements of the following: percent of patients with missing laboratory assessments, percent of patients with alarming laboratory values without follow up scheduled, mean adherence to immunosuppression, based on refill timeliness and estimated using the PDC, percent of patients with a significant drug interaction without a immunosuppressant level and percent of patients with hospital discharge or ED visit without follow up scheduled. These will be measured in all patients and compared between the intervention and control groups at monthly intervals.

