For the assessment of the functionality of the dashboard and the time required to complete the intervention, there will be no comparisons or modeling within this analysis; we will utilize standard descriptive statistics for these measurements, including mean (SD), median (IQR), proportion (%) and 95% confidence interval. Variables assessed for this outcome will be captured through input into the REDCap database by intervention pharmacists during the first year of the intervention. We will compile the total number of alerts the dashboard system generates at each site and assess the proportion of these that were deemed clinical relevant and actionable by the pharmacists. We will also determine the mean/median time required to complete the intervention on a daily basis and estimate the time per 100 patient days. We will conduct these assessments concurrently on a bimonthly basis for the first year of the intervention, which will allow us to modify the dashboard system's reporting thresholds and improve functionality if deemed necessary by the investigational team. We will also assess the overall functionality of the dashboard at the end of the first year to determine composite metrics. Based on our experience with the current system, after an initial bolus effect, we expect the dashboard will produce two to three new alerts per 100 patient days with one to two of these being relevant and actionable. We will utilize 95% confidence intervals actual versus expected rates.

We will handle missing data using several techniques including multiple imputation and maximum likelihood.⁶⁰ Missing data mechanisms will be examined using both univariate and multivariate methods. We will check for missing at random (MAR) by creating a missing indicator for each missing variable and study the predictors of missingness using logistic regression. If any of the fully observed covariates or outcomes becomes significant in the missing data model then we will use methods for MAR if we do not have any reason to believe that the missing data mechanism is not at random. The proposed GLMM models, which are mixed effects models for the longitudinal data analyses, can handle data that are missing at random (MAR) and provide robust estimates. For the cross-sectional data analysis plan, we will use

multiple imputation approaches and for categorical missing data we will use latent class based multiple imputation.^{57,60}

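### The dashboard-derived medication-safety outcomes have no fixed definition over the 24 months, because the team may change the dashboard's thresholds or components during year 1

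*Combined protocol and SAP*

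**What the plan says.** The objectives, in the synopsis and in section 1.2, take five medication-safety measures "based on automated reports for the transplant medication dashboard": missing labs, alarming labs without follow-up, adherence by PDC, a significant drug interaction without a drug level, and hospital discharge or ED visit without follow-up. Section 9.3.2 names the same source ("we will use the dashboard to provide monthly measurements of the following") and commits to a comparison: "These will be measured in all patients and compared between the intervention and control groups at monthly intervals". Sections 3 and 5.1 make this dashboard the tool through which the pharmacists intervene.

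Two places allow it to be changed while the trial runs. In section 9.3.2, if a component gives alerts of little clinical relevance, or too many alerts for each actionable one, "then the investigational team may decide to modify this component of the system". In section 9.4, concurrent review in year 1 allows the team to modify the dashboard's "reporting thresholds and improve functionality if deemed necessary by the investigational team". Neither gives a numeric rule. The evidence behind such a decision is what intervention pharmacists enter in REDCap during the first year.

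The two sections also differ on how often the review happens. Section 9.3.2 says "These measures will be assessed by investigators at quarterly intervals"; section 9.4 says "on a bimonthly basis for the first year of the intervention".

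Section 5.2 lists "Suppressing alerts" among the training sessions for pharmacists randomized to the intervention. Section 10.1 describes dashboard access for intervention-site pharmacists. It names hospitalizations, ER visits, costs and mortality as outcomes drawn from the CDW, and does not name these five measures.

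**The concern.** One system serves both as the intervention and as the instrument for five between-arm outcomes, and the plan allows the instrument to be retuned. The stated reason for retuning is an excess of alerts that need no action, so a change would tend to mean fewer flags. A fall in the monthly percentages could then reflect a new cut-off with no change in care, and a reader of the results could not tell the two apart.

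These measures carry some weight. The hypothesis in section 9.1 includes improved immunosuppressant safety alongside clinical outcomes, and section 14 plans a paper on process measures that covers adherence and safety events.

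**Working it through.** The plan states no figure to reproduce here. The check sets the sections side by side and then uses simple algebra.

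**1. Is the definition fixed?** Sections 1.2 and 9.3.2 name the dashboard as the source, and sections 9.3.2 and 9.4 allow it to change. No section freezes an outcome definition, says that a change reaches control-site reports on the same date, or says whether a suppressed alert still counts in the outcome report. Section 9.4 gives no model specific to these five measures, so nothing there would absorb a step.

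**2. How plausible is a change?** Section 9.4 expects 2 to 3 alerts per 100 patient days, of which 1 to 2 are relevant and actionable. The non-actionable share is 1 − actionable/alerts:
- matched ends: 1 − 1/2 = 50%, and 1 − 2/3 = 33%
- extremes: 1 − 2/2 = 0%, and 1 − 1/3 = 67%

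A third to a half of alerts would need no action at the expected rates. Whether that would trigger a change is unknown, because no limit is given. The opportunities in year 1 number 12/3 = 4 if reviews are quarterly, 12/2 = 6 if bimonthly means every two months, and 24 if it means twice a month.

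**3. Which outcomes can a threshold change move?**

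| Outcome | Criterion in section 5.1 | Exposure |
|---|---|---|
| Alarming labs without follow-up | Absolute and trajectory cut-offs | Direct |
| Drug interaction without a level | Drug list and triggers | Direct |
| Missing labs | None | Possible; the definition is not in the protocol |
| Mean PDC | Alert below 80%, but the outcome in 9.3.2 is a mean | Hardly any |
| Discharge or ED visit without follow-up | Triggered at discharge, no numeric cut-off | Hardly any |

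**4. What would a change do to the comparison?** Let p be the true proportion flagged, m the share of flags kept after a threshold change, and s the share suppressed. If suppressed flags leave the report, the observed proportion is p × m × (1 − s). The documents give none of these values; p = 10% in both arms, meaning no true effect, is an assumption.
- Same change in both arms, m = 0.7, s = 0: each arm reads 10% × 0.7 = 7%. The ratio is 7/7 = 1.00, and the series steps down by 3 points.
- The same change with an assumed true effect, 10% against 8%: the arms read 7.0% and 5.6%. The ratio stays at 0.80, but the difference shrinks from 2.0 to 1.4 points.
- Change at intervention sites only, m = 0.7 to 0.9: the ratio equals m, so 0.70 to 0.90.
- Suppression at intervention sites only, s = 10%, 33% or 50%: the ratio is 1 − s, so 0.90, 0.67 or 0.50.

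The last two cases return whatever is put in. They show the direction of the effect and say nothing about its likelihood or size.

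**The case against.** The strongest reply is that the text describes one system. Sections 9.3.2 and 9.4 speak of the dashboard and its components, not of settings by site or arm. Section 3 has intervention sites going live simultaneously and both arms followed in parallel, and the measures are compared within the same month. A common change therefore falls on both arms together. This stands: such a change does not by itself bias the ratio, provided it keeps the same share of flags in each arm.

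A reader might go further and infer that alert suppression lowers the intervention-arm figures. The documents do not support that. Suppression appears only as a session title in section 5.2; the operating manual (Appendix I) is not part of the text available, and its rules may settle the matter. The outcomes are patient-level percentages and a mean PDC from automated reports, not counts of open alerts, and nothing says that silencing an alert removes the patient from the report. Section 2.2 notes that in earlier dashboard work pharmacists handled missing labs by scheduling them or documenting non-VA care. That might act mainly in the intervention arm, but it too is inference.

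It can also be said that section 9.4 rules out comparisons for dashboard functionality, and that section 10.1 separates operational from research data. The first covers alert relevance and pharmacist time, whereas section 9.3.2 separately commits to comparing the five measures. The second leaves CDW computation open, since its list of outcomes is not worded as exhaustive, but it does not provide for it: the sections that define these measures name the dashboard.

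**Conclusion.** The point holds as a matter of definitions that can drift over time. Followed as written, the plan allows the meaning of at least two of the five secondary safety outcomes, alarming labs and drug interactions, to change during the first year. Missing labs may be affected as well. Mean PDC and discharge without follow-up hardly depend on thresholds; for PDC this relies on section 9.3.2, which reports a mean, since the lead-in to section 1.2 speaks of proportions of patients but gives no PDC cut-off.

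It would be tempting to conclude that the comparison is biased toward the intervention. That would need either changes made only at intervention sites or suppression that alters the outcome report. Neither is ruled out and neither is shown, so no size can be put on it.

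The primary outcome rests on CDW and CMS encounters (section 9.3.1), and the cost, graft and survival outcomes have their own sources, so none of these is affected. This should be corrected because a better method is cheap; it does not threaten the main result.

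**What to change.** In sections 9.3.2 and 9.4:
- Compute the five measures identically in both arms from CDW labs, medications, refills and encounters, with outcome code frozen at go-live and independent of alert or suppression status.
- Use the section 5.1 criteria as they stand at go-live where they exist. Pre-specify what section 5.1 does not supply: when a lab counts as missing, what counts as follow-up scheduled and within what window, and the window for an immunosuppressant level after an interaction.
- Let dashboard thresholds and components change for alerting only, and log the date and scope (which sites, which component) of each change.
- Reconcile the quarterly and bimonthly review schedules.

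The cost is some programming: section 10.1 already has these data elements queried from the CDW for the dashboard. The drawback is that outcome reports may differ from live dashboard counts, which the change log would help explain. The intervention itself is untouched.

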10 DATA COLLECTION AND QUALITY ASSURANCE

10.1 Data Collection and Management

There will two general types of data used for this proposal, which includes operational data used for the dashboard system and research data to assess the impact of the intervention on outcomes. Operational data for the dashboard will be captured through querying the national VA CDW operational database using the FRS environment and stored in VISN 7 space already approved and allocated for this project. These data elements include diagnoses, laboratory values, medication regimens, refill histories, provider types and health care encounters (hospitalizations, ER visits), gathered and queried on a daily basis. The pharmacists at intervention sites will access their site-specific dashboard information stored on the server through an end-user permission access link that will restrict which patients are visible to ensure appropriateness of access to the correct PHI.

For the research component of the proposal, data will be captured through the research CDW and housed within the VINCI environment. We will link the VA data to the SRTR registry and CMS claims data. The CDW will provide data to assess outcomes including hospitalizations, ER visits and costs, as well as mortality. CDW data will also be used to assess interventions by querying pharmacists' progress notes. The CMS data will provide non-VA health care utilization, including hospitalizations and ER visits, as well as non-VA cost estimates. The SRTR data will provide all baseline donor, recipient and transplant characteristics as well as clinical outcomes, including acute allograft rejection, graft loss and death. We will also capture pharmacist entered data, which will be their assessments of the dashboard system. We will deploy a web-based data entry system that the intervention pharmacists will use during the first year of the intervention to assess the dashboard functionality. Queries answered by intervention pharmacists will include the number of alerts received, how many were considered clinically relevant/actionable, time to conduct the intervention and general intervention types. This data will be captured through the use of the REDCap system.

After data is cleaned and completely ready for analysis, we will remove identifiers from the final datasets. This will minimize the risk of loss of confidentiality. All data will be stored on the VINCI system and only approved study personnel will have access to this data.

10.2 Quality Assurance

10.3.1 Training

Pharmacists randomized to the intervention will participate in a two-day intensive training conference held at the coordinating site (Charleston, SC). During this training, the dashboards functionality will be reviewed, along with the standard operating procedure manual which fully guides interventions. During this training conference, the intervention pharmacists will also complete competencies, using case-based questions. Pivotal sessions that occur during this conference will include: review of dashboard specifics, running the dashboard to create alerts, assessing clinical relevance of alerts, alert categories, interventions to address alerts, clinical and research documentation, provider collaboration mechanisms, motivational interviewing training and case-review sessions. The investigational team will lead these sessions and utilize local experts to deliver the presentations and lead the case-based sessions. The full training program will be developed after sites are randomized and the final dates of the training conference are agreed upon by study sites.

10.3.2 Quality Control

During the 24-month intervention period, we will have monthly teleconferences with the intervention pharmacists at the five sites to discuss and address issues with the dashboard and intervention. As an additional safety measure and to further ensure intervention fidelity, we will have experts available to discuss patient issues with sites participating in the intervention. These will include the PI, transplant nephrology, transplant hepatology and an internist. These experts are members of the study team and have full knowledge of the study. All interventions will be documented in the medical record using an approved note template, which has already been developed and is in use by pharmacists in VISN 7 and VISN 12. All interventions will be made under the approved scope of practice for the pharmacist or will be approved by the patient's VA primary care provider or other provider as appropriate. Thus, all interventions delivered as part of this study will be within usual care standards and practices.

As another quality assurance step, the coordinating site will oversee and review study interventions through querying the REDCap database system; these will be monitored by the PI and investigational team to ensure clinical appropriateness. This is particularly the case for interventions involving changes in immunosuppression regimens. If there are concerns with specific interventions made by study site pharmacists, these will be addressed on a case-by-case basis. During the course of the study, if an intervention pharmacist has a particular issue that is time sensitive and is unsure how to address it, they will have the ability to call and/or page the PI or investigational team, which includes expertise in transplant-related care. For non-urgent issues, pharmacists can send secure emails to investigational team members or bring up the issue during conference calls. Thus, there will be ample training and resources available to all intervention site pharmacists to ensure the study is conducted in a safe clinically appropriate manner with strong fidelity.

10.3.3 Metrics

The IOC will meet and review clinical events that are related to harmful issues, which may indicate harm, including hospitalizations, ED visits, graft loss and death. The PI and study team will also review the appropriateness of study interventions, which include medication changes, discontinuations and initiations. This includes immunosuppression medications.

10.3.4 Protocol Deviations

The SOP manual is provided to study site pharmacists with detailed instructions on how to deliver the interventions, including specific protocols to use once medication safety issues have been identified. These study site interventions will be monitored by the study site and PI. If any of these interventions are deemed to be inappropriate or deviations of the SOP manual and protocols, they will be further reviewed by the study site physicians and adjudicated. Following this, if the intervention is still considered as a protocol deviation, the study site pharmacist will be informed and corrective clinical action will be taken to address the deviation. This deviation will be documented. If patterns develop in which multiple protocol deviations are occurring at a particular study site, the IOC will be informed. They will review the issues and determine a corrective plan, which may include re-education and training, replacement of the study site pharmacist or discontinuation of the study at that particular site.

